### 4. \* List the study inclusion criteria:

Individuals must be 21-55, willing to provide informed consent, attend the lab sessions and abstain from tobacco/nicotine as required. They also must be able to provide a 'positive' (cassette) cotinine results at screening.

All participants must be healthy (determined by self-report), between the ages of 21-55, willing to provide informed consent, and attend the lab and abstain from tobacco/nicotine as required. Participants must agree to use designated products according to study protocol.

Cigarette Smokers: Must use  $\geq 10$  cigarettes per day and have not used an ECIG in the past 30 days and who have never used an ECIG daily for one week. Cigarette smokers must have a CO level at screening of at least 15 ppm and a 'positive' cotinine cassette result to verify nicotine use.

E-Cigarette Users: Must use ECIG  $\geq 3$  months,  $\geq 1$  ml of liquid per day or approximately one cartridge or one pod, at a nicotine concentration of  $\geq 3$  mg/ml and have not used tobacco cigarettes in the past 30 days. E-cigarette users must also have a 'positive' cotinine cassette results to verify nicotine use.

Please note that beginning July 1, 2020, per HB1570, we will recruit individuals aged 18-55. This law "Provides an exception to the law prohibiting possession of tobacco products, nicotine vapor products, or alternative nicotine products by a person less than 21 years of age when such possession is part of a scientific study being conducted by an organization for the purpose of medical research to further efforts in cigarette and tobacco use prevention and cessation and tobacco product regulation, provided that such medical research has been approved by an institutional review board pursuant to applicable federal regulations or by a research review committee." We will not enroll anyone aged 18 - 20 until on or after July 1, 2020.

### 5. \* List the study exclusion criteria:

Individuals with the following self-reported current, diagnosed medical condition(s) will be excluded automatically: heart-related conditions (e.g., recent heart attack/stroke, coronary heart disease), severe immune system disorders (e.g., HIV/AIDS, multiple sclerosis), respiratory disorders (e.g., COPD, asthma), kidney diseases, liver diseases (e.g., cirrhosis), or seizures.

Individuals with other self-reported current, diagnosed medical conditions (e.g., diabetes, thyroid disease, Lyme disease) will be considered for exclusion after consultation with the PI and medical monitor. Participants with any medical condition/medication that may affect participant safety, study outcomes, or biomarker data will be excluded based on these consultations.

Participants with self-reported current, diagnosed psychiatric conditions or who report current psychiatric treatment or psychotropic medication use will be excluded.

Individuals with past month use of cocaine, opioids, benzodiazepines, and methamphetamine. Individuals who report using marijuana greater than 15 days in the past 30 and/or alcohol greater than 25 days in the past 30 days will be excluded. Participants who choose not to answer question related to inclusion/exclusion criteria will be excluded.

Women will be excluded if they are breast-feeding or test positive for pregnancy (by urinalysis) at screening.

Participants who weigh less than 110 pounds will also be excluded. Those who intend to quit tobacco/nicotine use in the next 30 days will be excluded and referred to cessation treatment. Individuals who report using any other tobacco products (other than what is permitted per the inclusion criteria) on a weekly or more frequent basis will be excluded.

In addition, participants who have previously participated in a study with exactly the same manipulations of ECIG type, setting, and liquid concentration will be excluded. Specifically, participants who have participated in HM20012696 will not be eligible to participate in this protocol. Staff from this protocol will work with staff from HM20012696 (who are also listed on this protocol) to assure that there is no cross-participation between participants.

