In addition, non-invasive computerized monitoring equipment allows for minute-by-minute, real time monitoring of participants' heart rate and blood pressure (BP). Research personnel are trained to alert the research nurse if heart rate exceeds 120 beats per minute, if systolic BP exceeds 150 mm Hg, or if diastolic BP exceeds 100 mm Hg. Individuals whose heart rate and/or BP levels remain elevated will be monitored continually by the nurse, and if necessary emergency responders will be notified. Emergency medical coverage is available via the emergency room that is a half block away from the CBPL.

In the case of nicotine abstinence symptoms, the project products will possibly alleviate these risks. Participants will be provided with water at all times.

The risk of seizures is minimized by excluding participants with any history of seizures, and by having a full-time RN available, as well as monitoring of vital signs. In addition, some of the reported seizures occurred in users who were using other substances such as marijuana or amphetamines—the risk of seizures in this study is reduced as we are administering nicotine and no other substances.

The risk of respiratory illnesses related to ECIG use is minimized by the limited ECIG use that occurs in each session

(10 puffs plus a 90 minute ad lib use period). Participants are informed about recent reports of ECIG-related respiratory illnesses, and that most of the cases have been related to vaping THC. Participants are also informed that the Centers for Disease Control and Prevention advises that e-cigarette, or vaping products are unsafe for use by youths, young adults, or women who are pregnant and that adults who do not currently use tobacco products should not start using e-cigarette, or vaping, products. Participants are also advised to monitor themselves for symptoms and to seek medical attention if they have concerns. In addition, we will ask about respiratory and gastrointestinal symptoms at screening and before each session begins. Answers given at the beginning of each session will be compared to the participants' previous answers, and if any symptoms have increased, [name] will be asked to review the symptoms. In some cases, we may contact [name] to determine if a session can proceed.

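### The exclusion criteria cover seizures only as a current, diagnosed condition, while the risk section says that any history of seizures is excluded

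*Combined protocol and SAP*

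**What the plan says.** Study Population, item 5, sets up an automatic exclusion: "Individuals with the following self-reported current, diagnosed medical condition(s) will be excluded automatically". The list names heart, immune, respiratory and kidney conditions and ends with "liver diseases (e.g., cirrhosis), or seizures". It does not mention a history of seizures.

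Two more sentences in item 5 deal with conditions outside the list. Other current, diagnosed conditions "will be considered for exclusion after consultation with the PI and medical monitor". The next sentence is broader: people with any condition or medication "that may affect participant safety, study outcomes, or biomarker data will be excluded based on these consultations".

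The inclusion criteria (item 4) add a general requirement: "All participants must be healthy (determined by self-report".

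Risks, Discomforts, Potential Harms and Monitoring, item 2, explains how seizure risk is handled. It says "The risk of seizures is minimized by excluding participants with any history of seizures". It also relies on a nurse being on hand and on vital-sign checks during sessions, and it adds that "the risk of seizures in this study is reduced as we are administering nicotine and no other substances". Item 1 of the same section says that seizures in e-cigarette users have been reported in people with a seizure history, in people using other substances, and in others. The consent text reproduced in Behavioral Intervention Details, item 2, names seizures as a risk.

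**The concern.** Item 5 is the rule that staff apply at screening. The risk section is the account of participant protection given to the ethics board. On seizures the two describe different populations: one is limited to a current diagnosis, the other covers any past event. If staff follow item 5 as written, someone with past seizures and no current diagnosis can enrol, although the risk section says that such a person is excluded.

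The protocol treats this as a real risk. It warns participants about seizures and identifies people with a seizure history as one of the groups in which e-cigarette-related seizures have been reported. It does not say that history is the only such group.

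**Working it through.** The plan gives no figure on this point, so there is nothing to recompute. The check is a comparison of the current texts, none of which is amendment-log or superseded wording.

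**Step 1: apply each rule to the same three people.**

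| Person at screening | Exclusion list (Study Population, item 5) | Risk section (Risks, item 2) |
|---|---|---|
| Current, diagnosed seizure condition | Excluded automatically | Excluded |
| Recent seizure, no current diagnosis | Unclear; may be caught if the list is read loosely | Excluded |
| Past seizures, no current diagnosis | Not excluded automatically | Excluded |

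The third row is a direct conflict. The second depends on how strictly the opening words of the list are read.

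**Step 2: see whether another written rule covers the third row.**

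- *General health (item 4).* Health is judged by self-report. Someone whose last seizure was long ago can truthfully report being healthy.
- *Consultation clause (item 5).* Its first sentence concerns other current, diagnosed conditions and only opens the question of exclusion. Its second sentence is wider and could reach a past seizure or a medication taken for it, but exclusion still depends on the outcome of the consultation. The risk section states exclusion as a fact.
- *Symptom checks.* Risks, item 2, describes questions on respiratory and gastrointestinal symptoms at screening and before each session. Study Procedures, item 6, describes questions on symptoms since the last visit. These checks serve another purpose and are not described as asking about past seizures.

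None of these makes exclusion automatic for a past seizure.

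**Step 3: see what the risk section relies on.** It gives four seizure mitigations: the history exclusion, the nurse, vital-sign monitoring, and giving nicotine and no other substance. Of these four, only the history exclusion acts before enrolment, and it is the one that item 5 words more narrowly. The count applies to that paragraph alone. Item 5 also excludes past-month methamphetamine use and marijuana use on more than 15 of the past 30 days. Those rules also act before enrolment, on substance use that the risk section connects with seizures. The inconsistency does not depend on the count.

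**The case against.** The strongest reply is that the form has no separate protocol behind it, so its parts should be read together: item 5 names seizures and the risk section supplies the scope. The exclusion list also includes recent heart attack or stroke, which are past events, so its opening words are evidently not applied strictly. Seizures are listed as events and not as a disorder. The wider safety sentence in item 5, read with the risk section, makes any outcome other than exclusion hard to justify. Finally, the registry questions cover health issues (Secondary Data/Specimen Details, item 1) and a Health Information Form is completed at screening (Study Procedures, item 6). Either may already ask about lifetime seizures.

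Part of this stands. The authors' intention is clear from the risk section, and practice may already match it. The forms are not reproduced, so this cannot be settled from the documents.

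The rest does not remove the conflict. The heart attack and stroke example extends the list to recent events at most, which is short of any history. The safety sentence still works through consultation. Even if a form asks about lifetime seizures, item 5 attaches no automatic exclusion to a person who reports past seizures without a current diagnosis. Reading the two sections together shows what was meant, but the criterion that staff apply should say it.

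**Conclusion.** The concern holds. As written, the exclusion criterion is narrower than the safeguard stated in the risk section, and a person with past seizures and no current diagnosis falls between them.

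The severity is minor. No endpoint, analysis or sample size is affected. The documents do not say how common such people are among those screened, so no number affected and no probability of harm is claimed. The conclusion rests on the ordinary reading that the opening words of the exclusion list govern every item in it. It is a conclusion about the written rules; whether screening already excludes these people in practice is unknown.

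**What to change.** In Study Population, item 5, take seizures out of the list of current, diagnosed conditions and make any history of seizures a separate automatic exclusion, matching Risks, item 2. Then check that the registry screening questions and the Health Information Form ask about lifetime seizures, and add the question where it is missing.

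The two sections could also be reconciled by narrowing the risk section to current diagnoses. That would weaken a stated protection, so widening the exclusion is the better correction.

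The cost is one text amendment, a check of two forms and an unquantified number of extra screen failures. Study Population, item 3, allows up to 300 consents for 136 completers, which leaves 300 − 136 = 164 places. Those places must also cover every other screen failure and dropout. The target of 136 completers and the analysis stay as they are.

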After screening and informed consent, eligible participants will enroll in this study, which is modeled on our previous work (e.g., Spindle et al., 2016; Hilier et al., 2017). A total of 136 participants (68 cigarette smokers and 68 experienced ECIG users) are needed to complete the study. Once enrolled, participants will attend the lab for six additional experimental sessions (approximately 4 hours each) where they use an "open system" ECIG (Kanger Sub Box Mini) set to either 15 watts or 30 watts, which will contain either 10mg, 15 mg, or 30 mg nicotine-containing liquid. The design of this study is within-subjects, thus, all participants will complete six sessions that differ by the combination of watts and liquid concentration. Sessions will be ordered by Latin-square. The sessions will occur no more than 2 days per week and will be separated by at least 48 hours. The approximate total time that participants will be in the laboratory is 24.5 hours (30 minutes for screening and 24 hours for sessions). This does not include the 12 hours before each session that we ask participants to abstain from and nicotine/tobacco containing products.

During each session, participants will first complete a 10-puff product use bout, and then a 90-minute ad lib product use bout. Sessions will be preceded by 12 hours tobacco/nicotine abstinence (to measure the extent to which each device/liquid combination suppresses nicotine/tobacco abstinence symptoms), and session order will be ordered by Latin-square. In all sessions, participants will use topography-measurement equipment (a mouthpiece attached to the ECIG that is attached to a computer via tubing; the participant then puffs on the mouthpiece). Other outcomes include plasma nicotine, cardiovascular response, carbon monoxide level, and subjective effects (direct effects of the ECIG and nicotine, abstinence symptoms).

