More specifically, upon arrival at the laboratory for each session, participants' breath CO will be measured to ensure compliance with the overnight abstinence criteria (i.e. CO < or equal to 10 ppm for cigarette smokers, see Breland et al., 2006, or < or equal to 7 ppm for ECIG users). In addition, participants will be asked questions about symptoms experienced since the last visit. Once deemed abstinent, participants will begin a 1-hour waiting period. During this time, participants cannot eat or use their cell phones, although water, movies, and/or magazines will be provided. We have recently instituted this 1-hour waiting period in other studies, because we find, after looking at plasma nicotine levels which are analyzed months after participants complete studies, that some participants do not comply with the 12-hour nicotine/tobacco abstinence requirement. Adding this 1-hour waiting period ensures that all participants are abstinent for at least one hour before the session begins. After the 1-hour waiting period, an IV catheter will be inserted into a forearm vein of the participant, physiological monitoring equipment will be attached (arm blood pressure cuff, pulse oximotor placed on finger), and a 30-minute rest period will begin. This rest period allows us to measure resting heart rate and blood pressure immediately before product administration. A detailed timeline of the sessions is described below. Please note that because catheter insertion can be difficult, we will attempt to insert a catheter no more than three times in one day, and if all three attempts are unsuccessful, the session will be discontinued, with payment as outlined in the consent and compensation section.

The subjective questionnaires administered at each time point are as follows: Direct Effects of Vaping Questionnaire, Direct Effects of Nicotine Questionnaire, Hughes-Hatsukami Questionnaire, and the General Labeled Magnitude Scale. All of these questionnaires will be administered via computer or RedCap with the exception of the General Labeled Magnitude Scale, which may be administered via paper and pen, or via RedCap. At the end of each session, participants will also be asked one additional question: "Do you believe that you received nicotine today?" (Participants' answer will be entered into RedCap).

Experimental session timeline (times approximate):

Participant arrives, CO test to confirm tobacco abstinence, additional questions about symptoms asked  

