## Sample Collection Details

1. \* Select all of the types of samples that will be collected as part of this study.

- Amniotic Fluid
- Blood**
- Buccal Smears
- Saliva
- Tissue
- Urine**
- Other**
- None of the Above

2. \* If Other, please describe the type of sample being collected:  
Breath for carbon monoxide sample.

3. \* Select all of the methods of blood collection that will be utilized in this study:

- Individual Needle Stick(s)
- Indwelling Catheter Placed Solely for This Study**
- Indwelling Catheter Placed for Other Reason(s)
- Blood Collected at the Same Time as Non-Research Blood Collection(s)
- Other

4. \* In order to collect urine, will an indwelling catheter be placed solely for the research study:

- Yes
- No**

5. \* Describe how the sample will be collected and the collection schedule. For each type of sample, include information about

- The procedures that will be followed to collect the sample
- The role(s) of the individuals who will collect the sample
- The volume/size range of the sample
- The timing and frequency of sample collection

Urine will be collected at the in-person screening for this protocol to test for cotinine & pregnancy (pregnancy testing for women only). Urine will not be stored for later use.

Upon arrival at the CBPL for the research session, participants' breath CO will be measured to ensure compliance with the overnight abstinence criteria (i.e. CO less than or equal to 10 ppm for cigarette smokers and less than or equal to 7 ppm for experienced ECIG users).

Blood will be collected via intravenous catheter 4 times at each session (7 ml each time), for a total of 24 samples per person in the entire study (168 ml in total). Blood not be collected more than 2 times per week.

6. \* Will genetic testing or analyses be conducted on any of the samples:

- Yes
- No**

Date: Monday, February 8, 2021 3:17:36 PM

Print

Close

ID: HM20012738

View: SF2 - Active Internet Data Collection

HM20012738 - [name]

Effects of Electronic Cigarette Settings and Liquid Concentrations in Cigarette Smokers and Electronic Cigarette Users

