**Name**

- Signed Consent by Participant
- Signed Parent/Guardian Permission or Legally Authorized Representative Consent
- Signed Assent by Child or Decisionally Impaired Adult
- Verbal Assent by Child or Decisionally Impaired Adult
- Short Form Consent (limited applicability)
- None of the Above (select waiver below)

3. \* Select any waivers that apply to this consent / assent group:

- No Waivers Requested
- Waiver of All Consent or Some Elements in Consent Form
- Waiver of Parental Permission or Legally Authorized Representative Consent
- Waiver of All Assent by Child or Decisionally Impaired Adult
- Waiver of Signature on Consent/Permission Forms (waiver of documentation of consent)
- Exception from Informed Consent (for emergency research only)

4. \* Select all study team role(s) that will obtain consent / assent from this group:

- Principal Investigator
- Co/Sub-Investigator
- Medical or Psychological Responsible Investigator
- Lead Student/Trainee Investigator (leading their own project)
- Research Coordinator
- Research Nurse
- Consultant
- Research Assistant
- Pharmacist
- Statistician
- Regulatory Coordinator
- Trainee/Student(working on project)
- Other
- N/A: Requesting Waiver of Consent

5. \* Describe the consent procedures used for this group. Include when, where, and how consent / assent will be obtained both initially and, if applicable, during ongoing participation in the study:

Consent for this study will be obtained in the CBPL, at the in-person screening visit. Consent will be ongoing and assumed when a participant makes and completes follow up appointments. Lab staff will call the participants the day before their scheduled appointment and remind participants about upcoming appointments, go over study procedures, and check to make they are still interested in participating. This will occur before each appointment in which consent is assumed when participants show up for a session.

6. \* Describe the process for minimizing any potential perception of undue influence to participate when there is a pre-existing relationship between the participant and the researcher (e.g. treatment provider/patient; instructor/student; supervisor/employee, etc.):

The research study will be described fully to participants, and they will be allowed to ask as many questions as they

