## Pertinent and Incidental Findings

1. \* Is it likely investigators could discover a participant's previously unknown condition (e.g. pregnancy, disease, suicidal thoughts, wrong paternity, genetic results, or other findings that may be of importance to health or well-being) or if a participant is engaging in illegal or reportable activities:

- Yes  
 No

2. \* Describe what possible pertinent or incidental findings stemming from research-only procedures may be discovered.

During screening, we assess blood pressure. If a participant's blood pressure is high, our study nurse advises the participant to talk to their own doctor and to get treatment.

Participants will have to report marijuana usage as part of the screening process. Although this is an illegal activity, the research staff will not take any actions. If funded, this study will be automatically issued a certificate of confidentiality, which may provide additional protections for participants.

We will ask about respiratory and gastrointestinal symptoms at screening and before each session begins. Answers given at the beginning of each session will be compared to the participants' previous answers, and if any symptoms have increased, [name] will be asked to review the symptoms. In some cases, we may contact [name] to determine if a session can proceed.

3. \* Explain what actions or procedures research personnel should take to inform the PI of such a discovery :

Female participants will be tested for pregnancy during the in-person screening visit. If a female participant has a positive pregnancy test, she will be counseled by the study nurse to seek prenatal care.

Regarding respiratory and gastrointestinal symptoms, answers given at the beginning of each session will be compared to the participants' previous answers, and if any symptoms have increased, [name] will be asked to review the symptoms. In some cases, we may contact [name] to determine if a session can proceed.

4. \* Will findings be disclosed to participants and/or any other person/group outside of the study team?

- Yes  
 No

5. \* Describe a communication plan addressing:

1. What criteria will be used to determine which pertinent and/or incidental findings will be communicated, including the following for health related findings:

- The reliability of the tests/images, such as being done in a CLIA-certified lab,
- Whether the meaning and significance of the findings are known,

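### Pregnancy is tested only once, at screening, and no described step at the six later nicotine sessions is aimed at it: a low-priority, inexpensive safety improvement

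*Combined protocol and SAP*

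**What the plan says.** All references are to the combined protocol and SAP.

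- **Exclusion.** Study Population, item 5: "Women will be excluded if they are breast-feeding or test positive for pregnancy (by urinalysis) at screening".
- **Timing of the test.** Sample Collection Details, item 5: "Urine will be collected at the in-person screening for this protocol to test for cotinine & pregnancy". The same item says that urine is not kept. Pertinent and Incidental Findings, item 3, agrees: "Female participants will be tested for pregnancy during the in-person screening visit".
- **Exposure after the test.** Study Procedures, item 6, schedules six nicotine sessions: "The sessions will occur no more than 2 days per week and will be separated by at least 48 hours". It gives no maximum span and no limit between screening and session 1.
- **Checks around each session.** There is a breath CO test on arrival, and "participants will be asked questions about symptoms experienced since the last visit". Risks, Discomforts, Potential Harms and Monitoring, item 2, describes the content: "we will ask about respiratory and gastrointestinal symptoms at screening and before each session begins". Answers are compared with earlier ones, and increases are reviewed. Consent Groups, item 5, adds a telephone contact: "Lab staff will call the participants the day before their scheduled appointment and remind participants about upcoming appointments".
- **Withdrawal.** Item 5 of the Risks section allows withdrawal for safety concerns in general, failed catheter insertion or non-compliance. It does not name pregnancy.
- **Recognised risk.** Behavioral Intervention Details, item 2, warns of unknown risk to an embryo or fetus. Item 2 of the Risks section says participants are told of public-health advice that "e-cigarette, or vaping products are unsafe for use by youths, young adults, or women who are pregnant".

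**The concern.** A single negative urine test covers only pregnancies far enough along to be detected on that day. All six sessions come after it, over a period with no stated upper limit. The plan treats pregnancy as a reason not to take part and acknowledges possible fetal risk, and participants have no direct benefit to set against that risk. Yet it describes no later step meant to find a pregnancy that the screening test missed or that began afterwards. At stake is avoidable study exposure of a small number of women who do not know they are pregnant. No estimate, power figure or error rate is affected.

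**Working it through.** **1. Tests described.** One at screening (three sections agree) and none at the six sessions.

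**2. Later contacts, taken one by one.**
- Breath CO checks abstinence.
- The symptom questions are described as respiratory and gastrointestinal. Nausea, vomiting or fatigue could raise suspicion, but only if they occur.
- The reminder call covers appointments, procedures and continued interest.
- The session timeline lists questionnaires, CO tests, vital-sign monitoring and blood samples. Plasma nicotine is the blood outcome named.
- The general safety clause permits withdrawal once someone knows of a pregnancy.

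None of these is designed to detect pregnancy. Those that could help depend on symptoms, or on a woman who already knows and says so.

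**3. Shortest span from session 1 to session 6.** The inputs are six sessions, at least 2 days apart, at most 2 per week (Study Procedures, item 6).
- Calendar weeks: days 4, 6 | 8, 10 | 14, 16, so 16 − 4 = 12 days. With weekdays only it is 14 days.
- Any rolling 7 days: days 0, 2, 7, 9, 14, 16, so 16 days.

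**4. What retesting could find.** The documents give none of these inputs except the 136 completers (Study Population, item 3). Assumptions:
- women are 30%, 50% or 60% of 136, i.e. 40.8, 68 or 81.6;
- 3, 5 or 10 conceptions per 100 woman-years;
- 12, 35 or 60 days from screening to session 6 (12 days puts session 1 on the day of screening);
- a urine test stays negative for about 14 days after conception.

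Tests before every session could detect conceptions from 14 days before screening to 14 days before session 6. That window is as long as the time from screening to session 6, so the expected number is women × rate × days / 365. For an example rule (retest before session 1 if screening was more than 7 days earlier, then before any session 14 or more days after the last negative test), *days* becomes the day of the last retest.

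| Case | Test before every session | Example 7/14-day rule |
|---|---|---|
| Low | 40.8 × 0.03 × 12/365 = 0.04 | no retest: 0 |
| Middle | 68 × 0.05 × 35/365 = 0.33 | retests on days 10 and 25: 68 × 0.05 × 25/365 = 0.23 |
| High | 81.6 × 0.10 × 60/365 = 1.34 | retests on days 8, 22, 36 and 50: 81.6 × 0.10 × 50/365 = 1.12 |

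The middle case has sessions on days 10, 15, 20, 25, 30 and 35.

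**5. Fast schedules under the example rule, session 1 the day after screening.**
- Days 1, 3, 5, 7, 11, 13: no retest is triggered.
- Days 1, 3, 8, 10, 15, 17: one retest, on day 15 before session 5. Sessions 1 to 4 are not covered.

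The rule therefore matters mainly when sessions are spread out. Pregnancies of less than about 14 days are missed in any case.

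**6. Is the exposure already ordinary for these women?** Mostly, but not for every entrant (Study Population, item 4). Smokers must not have used an ECIG in the past 30 days, so aerosol from one is not a current exposure for half the planned sample. An ECIG user can qualify at 1 ml/day × 3 mg/ml = 3 mg of nicotine in liquid per day. At the study's 30 mg/ml, 3/30 = 0.1 ml of liquid contains that amount. These are liquid contents and not absorbed doses.

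**The case against.** The strongest case against has four parts.

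- **Nothing written is breached.** A reader might infer that the plan contradicts its own exclusion. It does not: the criterion refers to a positive test at screening, and the other two sections carry that out. This stands, and it is why the point is an improvement only.
- **The remedy may already exist.** A reader might also infer that women are never asked about pregnancy after screening, or never told to report one. The documents cannot support that. The symptom form, the Health Information Form and the consent form are not available, and the risk list taken from the consent form already mentions the embryo and fetus. This stands as a condition on the arrival question.
- **The benefit is tiny.** In the middle case the example rule finds 68 × 0.05 × 10/365 = 0.093 women before session 1 and 68 × 0.05 × 15/365 = 0.140 before session 4. It avoids 0.093 × 6 + 0.140 × 3 = 0.98 sessions out of 68 × 6 = 408, or about 0.24%, for up to 136 tests. This stands. Moreover, all the yield figures concern retesting. None measures the question, which still relies on self-report, or the withdrawal line, which detects nothing by itself.
- **Exposure is not new.** Entrants use nicotine daily, and each session follows 12 hours of abstinence and so partly replaces usual use. The Risks section, item 2, states that study exposure does not exceed ordinary exposure. This stands in large part, but step 6 and the protocol's own warning that the study liquid may be stronger than usual show that it is not assured for everyone.

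**Conclusion.** The point holds as a low-priority safety improvement. One pregnancy test is described, six sessions follow it over at least 12 to 16 days with no upper limit, and no described step or withdrawal criterion targets pregnancy. Expected yield runs from well under one to about one pregnancy in the whole study: 0.04, 0.33 or 1.3 with a test before every session, and 0, 0.23 or 1.1 under the example rule.

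These figures rest on assumed proportions of women, conception rates, durations and test window. One rate is applied to women up to age 55, which tends to overstate the yield. Counting completers only, when up to 300 may be consented, tends to understate it.

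Pertinent and Incidental Findings, item 5, also says that not knowing about a pregnancy carries no risk. A reader might take that as added support here. It is a separate wording matter, at odds with the fetal-risk warnings, and adds no weight to this point.

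**What to change.** 1. Add a question on possible pregnancy or a missed period to the symptom questions asked on arrival at each session, unless the symptom or consent forms already cover it.
2. Repeat the same urine test before a session when the last negative result is older than a limit set by the medical monitor and IRB. One example is more than 7 days before session 1, then 14 days or more before any later session.
3. In item 5 of the Risks section, state that a participant who reports a pregnancy or tests positive is withdrawn.

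**Cost.** One question per session, one line of text and an amendment. Under the example limits, each woman has 0 extra tests when session 6 falls 12 to 13 days after screening, 1 on the 17-day rolling schedule, at most 2 at 35 days and at most 4 at 60 days. That is up to 68 × 2 = 136 tests in the middle case and 81.6 × 4 ≈ 326 in the high case, each a few minutes of existing staff time. There are no new visits and no change to the design, the 68 per group, power or blood volume. The wording in Pertinent and Incidental Findings, item 5, can be corrected separately.
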